1.0 Objectives

1.1 Describe the purpose, specific aims, or objectives of this research. Specifically, explain why it is important to do the study.

Response: This study will test whether altering protein content in diet will change the levels of small molecules in blood and feces, with a major focus on amino acids. Additionally, we will test whether these dietary alterations affect gut bacteria. Many of the nutrients that individuals take in through diet can impact human health. More specifically, our group and others have shown that dietary amino acids enhance tumor growth through their use of these small molecules as a fuel source. We believe that reducing overall protein consumption will benefit cancer patients by reducing the amount of amino acids that tumors can use to support their growth. Before testing this, a study in healthy volunteers needs to be carried out to determine whether altering the amount of protein in their diet, impacts the levels of amino acids (and related metabolites) in blood or feces. By demonstrating that we can alter these small molecules in healthy individuals, it will provide us with information on the dietary formulation and duration of consumption required to achieve the biological effect we are seeking in future studies with cancer patients. To this end, we plan to carry out a study to determine whether modulating the amount of protein in specially formulated diets alters small molecules (e.g. amino acids) found in the blood and feces, as well as the types of bacteria found in feces, in healthy volunteers. Positive data from this study will provide the rationale for testing whether modulating dietary protein in cancer patients is beneficial.

1.2 State the hypothesis to be tested, if applicable.

NOTE: A hypothesis is a specific, testable prediction about what you expect to happen in your study that corresponds with your above listed objectives.

PROTOCOL TITLE:

Response: We hypothesize that modulating dietary protein content will alter blood and fecal metabolites and cause a shift in the types of bacteria found in the gut.

2.0 Scientific/Safety Endpoints

2.1 *Describe the scientific endpoint(s), the main result or occurrence under study.*

NOTE: Scientific endpoints are outcomes defined before the study begins to determine whether the objectives of the study have been met and to draw conclusions from the data. Include primary and secondary endpoints. Some example endpoints are: reduction of symptoms, improvement in quality of life, or survival. Your response should not be a date.

Response:

To determine whether reducing protein intake alters:

Circulating metabolites as determined by targeted metabolite profiling of blood.

Fecal metabolome as determined by targeted metabolite profiling.

Fecal microbiota as determined by 16S rRNA and metatranscriptomic analyses.

3.0 Background

3.1 *Provide the scientific or scholarly background, rationale, and significance of the research based on the existing literature and how it will contribute/fill in gaps to existing knowledge.*

Response: It is known that tumors have an affinity for taking up amino acids from circulation or nearby tissues to use as a fuel source, to enhance their growth. Work in rodents by our group and others, has shown that when the levels of amino acids are reduced in diet, tumor growth is slowed and tumors are more susceptible to anti-cancer therapies. There are currently limited dietary recommendations for cancer patients, which represents an urgent and unmet need. It is likely that reducing dietary protein will be beneficial, however this has not been tested. In advance of carrying out a study in cancer patients a study in healthy volunteers needs to be carried out to determine whether altering the amount of dietary protein impacts the levels of amino acids (or other metabolites) in blood or the intestine. By demonstrating that we can induce alterations in healthy individuals, it will provide us with the information on the dietary formulation and duration of consumption required to achieve the biological effect we are seeking in cancer patients, for future studies.

3.2 *Include complete citations or references:*

PROTOCOL TITLE:

Response: *Maddock et al., Nature, 2012*

Labuschagne et al., Cell Reports, 2014

Maddock et al., Nature, 2017

[name] et al., unpublished

4.0 Study Design

4.1 *Describe and explain the study design (e.g. case-control, cross-sectional, ethnographic, experimental, interventional, longitudinal, and observational). Indicate if there is randomization, blinding, control group, etc. If randomizing, explain how this will be achieved.*

Response: *The proposed study is experimental. Individuals will be provided a 'baseline' diet for 1 week then switched to a high protein diet for 2 weeks then to a low protein diet for 2 weeks. An additional 2 days will be allotted at the end of each feeding period to allow for sufficient time to collect samples) potentially adding an additional week to the entire study (See Figure 1 below). If subjects are able to provide samples immediately after completing a given feeding period, they will immediately be advanced to the next stage of the study. Therefore, the study will last from 5 to 6 weeks depending on the efficiency of sample collections. Samples will be collected after the acclimation period and after completion of the high protein diet period and after completion of the low protein period (see Figure 1 below). Therefore, individuals will serve as their own controls.*

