Following this period, low protein diets (0.8g/kg/day) will be devised and provided for the next 14-16 days (Figure 1). Fat content will be modulated to keep diets isocaloric while keeping carbohydrate content stable. Participants will choose between two 3-day cycle menus for each feeding phase. Meals will be prepared by [name], RD, Chef in a metabolic kitchen housed in SBU's Business Incubator at Calverton with the help of SBU dietetic interns. Meals will be prepared in batches, packaged and frozen at the incubator, then transported in a cooler with thermometers by members of the Nutrition Division to the Food Service Department at SBU Hospital. Meals will be kept frozen in freezers until the day they are provided to participants. Each day of the feeding period, dietetic interns will take all meals for all participants for that day from the freezers and place them in a cooler with a thermometer to bring them to a campus dining area. Logs of temperatures of coolers will be maintained daily, with temperatures checked every hour.

PROTOCOL TITLE:

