In order to provide meals, participants will come to room 3-064C in the HSC building on the East side of the Stony Brook University campus (conference room located in the office suite of the Division of Nutrition) ~~a semi-private area on the 2nd floor of the Student Activity Center~~ between 8:30-11AM to eat breakfast onsite and pick up other meals and snacks for the rest of the day, from a dietetic intern. Participants will be provided a closed envelope containing a form that will list their participant ID# and age in which they'll sign in and indicate if they've begun any new medications or been diagnosed with a disease since starting the study (form attached). Additionally, every Monday and Thursday, participants will be weighed using a digital scale in a ~~private area within the Division of Nutrition Suite on the 2nd floor of the Student Activity Center~~, in order to track changes in body weight while on the study. If weight changes greater than 2% of baseline, calorie content of the meals will be modified to avoid further weight changes. Food for the rest of the day will be provided in an insulated bag containing frozen cold packs and participants will be instructed to keep lunch and dinner in the insulated bag or a refrigerator until eaten. They will be instructed to heat the respective meals in a microwave until hot, prior to consumption. They will be instructed to take a picture of each meal before and after eating and upload the pictures via a Qualtrics-based survey, in order for the study team to estimate how much food has been eaten at each meal. Although participants will be instructed to only eat the food and beverages provided for the study, they will log any consumption of food or beverages not provided for the study via this same Qualtrics-based survey. Consumption of water, black coffee and tea will not be logged.

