During days 7-9, 24-26 and 41-43 (Figure 1) participants will provide a stool sample to be placed into a sterile container (provided by the study team) then placed into an opaque brown paper bag and brought to the Division of Nutrition Suite student health services within 1 hour, where it will be kept ~~cold in a cooler until refrigerated until picked up by the study team to be~~ stored at -80°C. On the same day as providing ~~At the same time~~ the stool sample ~~is delivered~~, blood will be drawn by a phlebotomist at Student Health Services to generate plasma. An order for the blood draw will be placed by a physician at Student Health Services. The physician will not have any interaction with the study subject. After the blood draw, the phlebotomist at Student Health Services will call and email a member of the [name] Lab to report the sample collection and samples will be kept at 4°C until picked up. ~~Stool and p~~lasma samples will be picked up by a member of the [name] Lab within 1 hour of being contacted. Plasma will be distributed into 2mL screw cap tubes in 4 equal aliquots and ~~stool sample will be cut in half and stored in two 50mL tubes and all samples will be~~ placed into a -80°C freezer until analysis. If a participant provides samples in the earlier part of the collection period (e.g. day 7) they may proceed immediately to the next phase of the study.

[figure not shown]

Figure 1. Experimental design.

PROTOCOL TITLE:

10.1 Describe what data, including long-term follow-up, will be collected.

NOTE: For studies with multiple data collection points or long-term follow up, consider the addition of a schedule or table in your response.

Response: Primary endpoints:

Circulating metabolite levels in blood

Fecal microbiota profiling by 16S rRNA analysis & metatranscriptomics

Fecal metabolite levels

☐ List, and upload, any instruments or measurement tools used to collect data (e.g. survey, scripts, questionnaire, interview guide, validated instrument, data collection form).

Response: These documents have been uploaded.

10.2 Describe any source records that will be used to collect data about subjects (e.g. school records, electronic medical records) and include the date range for records that will be accessed..

Response: N/A

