16.0 Data Management and Analysis

16.1 Describe the data analysis plan, including any statistical procedures. This section applies to both quantitative and qualitative analysis.

PROTOCOL TITLE:

Response: For our primary endpoint of measuring circulating amino acid levels, data will be transformed to reflect log2 fold change values at each of the 2 time points following administration of the experimental diets, compared to the levels at baseline. Paired t-tests will be used to determine whether significant changes occur.

16.2 If applicable, provide a power analysis.

NOTE: This may not apply to certain types of studies, including chart/records reviews, survey studies, or observational studies. This question is asked to elicit whether the investigator has an adequate sample size to achieve the study objectives and justify a conclusion.

Response: The statistical analysis for the primary aim of the study will compare circulating amino acid levels in subjects after consuming high or low protein diets for 2 weeks. We will enroll 14 subjects with the prediction that 10 will complete the study. A sample size of 10 subjects will allow 80% power to detect minimum differences of 0.996 standard deviations in plasma amino acid levels at 5% significance with the use of paired t-tests.

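### Everyone eats high protein first and low protein second, so the high-versus-low paired t-test cannot separate the effect of diet from change over time on study

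*Combined protocol and SAP*

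**What the plan says.** Section 4.1 describes one sequence for all: a baseline diet for a week, after which participants are "switched to a high protein diet for 2 weeks then to a low protein diet for 2 weeks". The form asks there about randomisation and a control group. The answer gives neither; the only control is within-person: "Therefore, individuals will serve as their own controls".

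Section 10.0 repeats the order. High protein (2 g/kg/day) follows acclimation, and then: "Following this period, low protein diets (0.8g/kg/day) will be devised and provided for the next 14-16 days". Blood and stool are collected "During days 7-9, 24-26 and 41-43". A participant who gives samples early may move straight to the next phase, and no washout is described.

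Sections 5.2 and 16.2 say that the primary analysis will "compare circulating amino acid levels in subjects after consuming high or low protein diets for 2 weeks", using paired t-tests. In section 16.1, "data will be transformed to reflect log2 fold change values at each of the 2 time points following administration of the experimental diets", each relative to baseline, and paired t-tests follow. No period term, second sequence or sensitivity analysis for time appears.

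The claims are causal. Section 1.2 states: "We hypothesize that modulating dietary protein content will alter blood and fecal metabolites". Section 2.1 asks whether cutting protein intake changes metabolites, section 21 speaks of showing that it lowers circulating amino acids, and section 1.1 makes positive data the rationale for a study in cancer patients.

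**The concern.** Using people as their own controls removes stable differences between them. It does not remove anything that changes between the second and third collections. Because low protein always comes last, a general downward drift in amino acids would look like the hoped-for fall, and an upward drift would hide a real one. Enrolling more people in the same order would only estimate the mixture more precisely.

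The protocol does have safeguards: breakfast on site, meal photographs, a log of outside food, removal for missed meals, and no assays until all subjects finish. These limit loss of adherence and assay drift, but not other change over time. One time-dependent element is written into section 10.0: "If weight changes greater than 2% of baseline, calorie content of the meals will be modified to avoid further weight changes". The documents do not say how often this is expected. At stake is whether a positive result can be attributed to protein content, which is the basis for the next study.

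**Working it through.** **The plan's own figure.** Inputs from sections 5.2 and 16.2: 10 completers, 5% significance, paired t-test, 0.996 SD, 80% power. Reading the SD as that of the paired difference, the noncentrality is 0.996 × √10 = 3.150 on 9 df. Two-sided power is 80.0%, so the figure reproduces (a one-sided test would give 89.5%). The power statement is sound; the difficulty is what the test estimates.

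**What is estimated.** Let B, H and L be a person's log2 levels after baseline, high and low protein. Then L − H = diet effect + time change + error, with the same coefficients for everyone. The design matrix for the two effects has rank 1, so only their sum is estimable. With both orders present the rank is 2.

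**Role of baseline.** (L − B) − (H − B) = L − H, so the fold-change step leaves the high-versus-low test unchanged.

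**Size, at assumed shifts.** Diet effect zero, n = 10, two-sided 5%, noncentrality = shift × √10:

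| Shift (SD of paired difference) | Noncentrality | Significant, fixed order | Of which in direction of drift | Randomised 5/5, period-adjusted (8 df) |
|---|---|---|---|---|
| 0.3 | 0.949 | 13.6% | 13.4% | 5.0% |
| 0.5 | 1.581 | 29.3% | 29.3% | 5.0% |
| 0.75 | 2.372 | 56.2% | 56.2% | 4.9% |

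The fixed-order columns are exact. The last column is from 200,000 simulated trials, which gave 13.7%, 29.3% and 56.4% for the fixed order.

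**Price of randomising.** With a and b completers per order, the standard error of the diet effect is 0.5 × √(1/a + 1/b) SD on a + b − 2 df. If 4 of 14 drop out at random from 7/7, there are C(14,4) = 1001 possible dropout sets.

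| Split | Standard error | Power at 0.996 SD | Detectable at 80% | Probability of split |
|---|---|---|---|---|
| 5/5 | 0.316 | 78.7% | 1.012 SD | 441/1001 = 44% |
| 6/4 | 0.323 | 77.1% | 1.033 SD | 490/1001 = 49% |
| 7/3 | 0.345 | 71.6% | 1.104 SD | 70/1001 = 7% |

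**Carry-over.** Let cH and cL be the carry-over of the high and low diets into the following phase. In the fixed order the bias in L − H is the time change plus cH. In the randomised design it is (cH − cL)/2. With cH = c and cL = 0 the carry-over bias falls from c to c/2; with cH = c and cL = −c it stays at c, toward no difference.

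**A contrast that the fixed order allows.** Collections are nominally 17 days apart, so linear drift cancels in H − (B + L)/2. Over the stated windows the residue is at most 26 − (7 + 41)/2 = 2 days of drift.
- Under equal variances and correlations, its variance is 1.5 against 2 for L − H in the same units, so its SD is √0.75 = 0.866 of that of L − H.
- With a linear dose-response and habitual intake x g/kg, it captures [2 − (x + 0.8)/2] / 1.2 = 1 − (x − 0.8)/2.4 of the high–low effect.
- The detectable high–low difference is 0.996 × 0.866 divided by that fraction: 0.86 SD at x = 0.8, 1.15 SD at 1.4 and 1.73 SD at 2.0. The range of x is assumed.

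**The case against.** Section 16.1 can be read more widely, as testing each diet against baseline as well. A rise on high protein followed by a fall below baseline on low protein could not come from monotone drift alone, and the contrast H − (B + L)/2 can be built from the two fold changes already planned. That is true and is the basis of the fallback. But each comparison with baseline is itself confounded with time, no analysis of the pattern is specified, and baseline protein differs between people because acclimation meals mimic each person's usual diet.

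The order may also be deliberate: section 2.1 asks about reducing protein, and high-then-low is a reduction. The protocol does not give this reason, and it would not remove the confounding.

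Nothing in the documents suggests a drift as large as 0.75 SD over about two weeks in healthy young adults on supplied meals, and the calorie rule is meant to stabilise weight. This stands: the error rates illustrate assumed shifts and do not predict what will happen. The confounding itself does not depend on their size.

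Randomising adds no washout and does not cure unequal carry-over. It also complicates the rule in section 19.3 that keeps the first two collections from late withdrawals, since these would then mix two comparisons. Both points stand as limits on the remedy. Finally, the fallback's detectable differences are approximate, because variation in habitual intake would add variance that they do not count.

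**Conclusion.** The concern holds. As planned, the primary test estimates diet plus time, while the protocol attributes the result to protein content. That conclusion follows from the design alone. How far it could mislead depends on a drift that the documents do not quantify: between about 14% and 56% false-positive results across the assumed shifts of 0.3 to 0.75 SD, with an opposite drift masking a true fall. The comparison with randomised order assumes an additive period effect and no unequal carry-over. This should be settled before feeding starts, because the order cannot be randomised afterwards.

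**What to change.** **Preferred.** After acclimation, randomise the order of the two existing diets 1:1, seven per order, from a concealed list in permuted blocks whose sizes sum to 14 (for example 4, 4 and 6). Analyse the within-person low-minus-high log2 difference adjusted for period. State in section 19.3 how participants with only two collections will be used. Report unequal carry-over and weaker second-phase adherence as remaining limitations, partly mitigated by sampling at the end of each phase.

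**If the order stays fixed.** Say so in section 4.1 with the reason. Limit conclusions under sections 1.1, 1.2 and 21 to changes over the feeding sequence. Pre-specify H − (B + L)/2 as a sensitivity contrast with its linear-drift assumption stated.

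**Cost.** The preferred route needs a protocol amendment and a 14-line allocation list; diets, phase lengths, blood draws and enrolment are unchanged, and the loss of power is about one percentage point at a 5/5 split. Both diets would have to be served in parallel. That looks feasible given batch-frozen meals (section 10.0) and a three-month enrolment period (section 11.1), but this is an inference that the study team should confirm. The fallback needs text changes only and no extra samples.

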5.0 Local Number of Subjects

5.1 *Indicate the total number of subjects who will be enrolled or records that will be reviewed through Stony Brook.*

Response: *We will enroll 14 subjects with the prediction that 10 will complete the study. Given that the subjects are healthy volunteers, medical records will not be searched but instead subjects' health status will be evaluated through a brief health questionnaire (provided as an attachment to this protocol application).*

5.2 *If this study is only being conducted through Stony Brook, provide statistical justification (i.e. power analysis) for the number of subjects provided in 5.1 above. If qualitative research, so state, and provide general justification for the total number of subjects proposed.*

Response: The statistical analysis for the primary aim of the study will compare circulating amino acid levels in subjects after consuming high or low protein diets for 2 weeks. We will

PROTOCOL TITLE:

enroll 14 subjects with the prediction that 10 will complete the study. A sample size of 10 subjects will allow 80% power to detect minimum differences of 0.996 standard deviations in plasma amino acid levels at 5% significance with the use of paired t-tests.

5.3 If applicable, indicate your screen failure rate, i.e., how many subjects you expect to screen to reach your target sample.

Response: We will have 2 layers of screening during recruitment. The initial screening will be Qualtrics-based and done remotely upon a potential subject viewing an advertisement and accessed from a QR code on the paper announcements or as a link in the email announcements. This initial screen will exclude potential participants if they don't meet the basic eligibility criteria (screening survey attached to this protocol). This will be done anonymously if they don't pass the survey. We predict that about 40 people will take the screening survey and 50% of the individuals who take this initial survey will not be eligible. The second screen will occur in person and consist of individuals completing a health questionnaire and being provided a detailed description of study design and requirements to participate in the study. The detailed description will include a review of the two choices of menus/ingredients for each phase of the study, followed by written agreement by the subject to eat the foods provided. Of the 20 people remaining who will undergo the in-person screening, we predict that approximately 20% of those individuals will be excluded, resulting in our goal of enrolling 14 people to result in 10 people having completed the entire study.

5.4 Justify the feasibility of recruiting the proposed number of eligible subjects within the anticipated recruitment period. For example, how many potential subjects do you have access to? What percentage of those potential subjects do you need to recruit?
Response: In light of the fact that we will be targeting SBU students for recruitment, there is a pool of approximately 25,000 individuals. Therefore we believe that reaching our goal of enrolling 14 will be feasible.

